## 4.0 SUBJECT SCREENING & RECRUITMENT

Patients enrolled on the 20030165 clinical trial are eligible for this trial and will be offered enrollment to this study.

## 5.0 PATIENT SELECTION

### 5.1 Inclusion Criteria

- 5.1.1 Enrolled on the 20030165 clinical trial.
- 5.1.2 Ability to understand and willingness to sign a written informed consent document.

### 5.2 Exclusion Criteria

- 5.2.1 Patients who were discontinued from 20030165 for any reason prior to the completion of protocol-specified treatment (e.g. withdrawal of consent).

- 5.2.2 Uncontrolled, intercurrent serious illness including but not limited to ongoing or active infection, symptomatic congestive heart failure, unstable angina pectoris, and/or cardiac arrhythmia likely in the judgment of the PI to interfere with clinical study requirements.
- 5.2.3 Psychiatric illness/condition likely in the judgment of the PI to limit compliance with clinical study requirements.

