## PROTOCOL SYNOPSIS

|                                    |   |
|------------------------------------|---|
| Protocol Title              | Long-term Follow-Up and/or Continued Thalidomide (THALOMID®) Maintenance Therapy for Patients Enrolled on Clinical Trial 20030165   |
| Targeted Patient Population | Patients enrolled on Clinical Trial 20030165.   |
| Study Design                | 
The study is designed to provide long-term follow-up and/or to offer continued maintenance thalidomide (THALOMID®) therapy to those patients enrolled in 20030165.
 
Group A: Patients who achieved CR in 20030165 and continue to receive maintenance Thalidomide.
 
Group B: Patients who achieved CR in 20030165, but are not receiving maintenance Thalidomide.
 
Group C: All other patients enrolled in 20030165 who expired or experienced disease progression.
 |
| Treatment Schema            | Thalidomide (THALOMID®) will be administered as per standard of care guidelines to Group A; in compliance with REMS™ program requirements.  |
| Study Duration              | 
Patients in Group A, B and C will be followed until withdrawal of consent, or death.
 
Note: All other patients in Group C who expired on 20030165 will also be included in all analyses.
  |
| Follow-up Required          | All patients will be followed annually by telephone or in-person visit(s), until death or withdrawal.   |
| Objectives                  | 
Primary Objective: To provide long-term follow-up and/or offer continued maintenance thalidomide (THALOMID®) to patients enrolled in 20030165 .
 
Secondary Objective: To continue to evaluate objectives specified for 20030165 (please refer to 20030165 for details).
  |
| Expected Number of Patients | 
Group A: 2
 
Group B: 12
 
Group C: 8
   |
| Expected Number of Centers  | 1-Sylvester Comprehensive Cancer Center (SCCC)
Note: SCCC is inclusive of the constituent satellite sites.  |

|  |  |
|--|--|
| Expected Duration of the Protocol | At least 5 years.  |
| Inclusion Criteria                | 

1. Enrolled on the 20030165 clinical trial.

2. Ability to understand and willingness to sign a written informed consent document.

  |

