### 17.3 Informed Consent and Permission to Use Protected Health Information

It is the responsibility of the investigator to obtain written informed consent from each subject participating in this study after adequate explanation, in lay language, of the methods, objectives, anticipated benefits, and potential hazards of the study. The investigator must also explain that the subject is completely free to refuse to enter the study or to discontinue participation at any time (for any reason) and receive alternative conventional therapy as indicated. Prior to study participation, each subject will sign an IRB approved informed consent form and receive a copy of same (and information leaflet, if appropriate). For subjects not qualified or able to give legal consent, consent must be obtained from a parent, legal guardian, or custodian. The investigator or designee **must** explain to the subject before enrollment into the study that for evaluation of study results, the subject's protected health information obtained during the study may be shared with the study sponsor, regulatory agencies, and the IRB. It is the investigator's (or designee's) responsibility to obtain permission to use protected health information per HIPAA from each subject, or if appropriate, the subjects' parent or legal guardian.

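### Exclusion 5.2.1, read literally, shuts living patients who progressed before completing 20030165 treatment out of the annual survival follow-up that the protocol assigns to Group C

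*Protocol*

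**What the plan says.** Section 5.2.1 of the protocol, and the first exclusion criterion in the synopsis, exclude "Patients who were discontinued from 20030165 for any reason prior to the completion of protocol-specified treatment (e.g. withdrawal of consent"). Section 6.0 requires all eligibility requirements to be reviewed, with a signed checklist, before a patient enters the study.

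The synopsis defines Group C as "All other patients enrolled in 20030165 who expired or experienced disease progression", and Section 7.0 describes it in the same way. Neither requires that 20030165 treatment was completed. The expected count is 8.

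On follow-up, the synopsis says "Patients in Group A, B and C will be followed until withdrawal of consent, or death". Section 12.4 sets yearly survival contact for Group C by telephone or visit, and Section 12.6 repeats that it ends only at death or when consent is withdrawn.

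Section 3.2 measures OS from 20030165 enrollment and censors patients who are alive or lost at the date last contacted or last known alive. Section 2.1 gives long-term follow-up of 20030165 patients as part of the primary objective.

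**The concern.** One rule assigns a patient to Group C and schedules yearly contact; another bars the same patient from the study. The patient concerned progressed while still on 20030165 treatment, stopped for that reason, and is alive. Because follow-up ends when consent is withdrawn, living Group C patients are evidently expected to consent to this study and so to pass Section 5.

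A coordinator who works from the checklist would turn this patient away. Survival information would then stop at the last 20030165 contact. The patients lost are those who failed early, so the censoring is unlikely to be independent of prognosis. In a study whose purpose is long-term follow-up, that is the wrong group to lose.

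**Working it through.** **Inputs.** Expected counts from the synopsis: Group A 2, Group B 12, Group C 8. Section 7.0 gives 14 for Groups A and B together. The protocol states no alpha, power or effect size, so there is no sample-size figure to test.

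**Step 1, the plan's own figure.** A + B = 2 + 12 = 14, which matches Section 7.0. The total is 14 + 8 = 22, and Group C is 8/22 = 36.4% of it.

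**Step 2, the rules set against each type of Group C patient.**

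| Patient | In Group C? | Barred by 5.2.1? | Yearly contact due? | Conflict over follow-up |
|---|---|---|---|---|
| Died on 20030165 | Yes | Not material | No | None |
| Alive, progressed after completing treatment | Yes | No | Yes | None |
| Alive, progressed and stopped before completing treatment | Yes | Yes | Yes | **Yes** |

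Only the third row conflicts.

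**Step 3, how many.** Let d be the Group C patients who had died and c those alive who completed treatment before progressing. The number affected is m = 8 − d − c. Neither d nor c is given, so m runs from 0 to 8, or 0 to 36.4% of 22. Reaching 8 needs d = 0 and c = 0. The synopsis makes express provision for Group C patients who died, so that upper end is only an arithmetic bound.

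**Step 4, effect by endpoint.**
- PFS (Section 3.1): progression is an event. An affected patient has already progressed, so the PFS time is fixed and later contact cannot change it.
- OS (Section 3.2): the patient is alive at the last 20030165 contact. Without yearly contact, a later death may never be recorded and the patient is censored at that date. Those still at risk are then weighted towards Groups A and B, which consist of patients who reached complete response. If the risk of death is higher after early progression (an assumption, though a mild one in this disease), the later part of the OS curve is biased upward.

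The size of the OS bias cannot be computed, because m, the contact dates and the post-progression survival are not in the document.

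**The case against.** The strongest reply is that the conflict may be empty. Whether any Group C patient was discontinued before completing treatment depends on how 20030165 defines completion and on its disposition data, neither of which is shown. If 20030165 regarded stopping at progression as completing treatment as specified, 5.2.1 would not catch these patients. In addition, OS is secondary, and Section 15.0 plans no formal analysis and leaves any integration with 20030165 to the principal investigator. All this limits the weight of the point. It does not remove the clash, because the exclusion applies whatever the reason for stopping and nothing exempts progression.

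A reader might infer three stronger things that the text does not support.

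- *That Section 5 strips early failures from the PFS, OS and response sets and inflates the results.* Sections 3.1.1 and 3.2.1 name 20030165 enrollment in the same clause and ask that therapy was received, not completed. The synopsis adds that "All other patients in Group C who expired on 20030165 will also be included in all analyses", and Section 7.0 says the same of Group C as a whole. Section 7.0 does use the word eligible for the 14 rollover patients, which is a reason to tidy the wording but does not outweigh those statements.
- *That the consent requirement contradicts Group C.* Section 5.1.2 asks for "Ability to understand and willingness to sign a written informed consent document" and Section 17.3 says "Prior to study participation, each subject will sign an IRB approved informed consent form". The dead cannot sign, but they can be read as contributing existing 20030165 data for analysis only. For living patients the requirement agrees with 12.4 and 12.6, which presuppose consent.
- *That Section 4.0 contradicts 5.2.1.* It says "Patients enrolled on the 20030165 clinical trial are eligible for this trial and will be offered enrollment to this study". This is a general description of the recruitment pool, narrowed by the criteria that follow it, which is ordinary drafting.

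**Conclusion.** The point holds in a narrow form. Section 5.2.1 and its synopsis copy conflict with the Group C definition and with the follow-up in the synopsis, 12.4 and 12.6, for living patients who progressed before completing 20030165 treatment. The consequence is selective loss of OS follow-up, probably in the favourable direction, in an unstated number of patients between 0 and 8. The primary PFS endpoint is not affected, nor is any sample-size figure.

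This rests on three assumptions: that stopping for progression counts as discontinuation before completion, as the breadth of the wording suggests; that site staff apply Section 5 to living Group C patients; and that early progressors have a higher risk of death than those who remain under follow-up. If the first fails, or if no such patient exists, there is no numerical effect and only the inconsistency in wording remains.

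**What to change.** Amend 5.2.1 and the matching synopsis criterion so that they agree with the Group C definition and with 12.4 and 12.6: having stopped 20030165 early because of progression should not bar a consenting living patient from Group C survival contact.

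Add one sentence saying that Section 5 governs prospective enrollment into this study only and does not restrict the sets in 3.1.1 and 3.2.1. Those sets are the 20030165-eligible, treated patients, including Group C, as the synopsis and Section 7.0 already imply.

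The cost is a short wording amendment and a few more yearly contacts. OS may come out slightly less favourable than with these patients censored early. The analysis sets, as most naturally read, do not change.

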| Exclusion Criteria                | 

1. Patients who were discontinued from 20030165 for any reason prior to the completion of protocol-specified treatment (e.g. withdrawal of consent).

2. Uncontrolled, intercurrent serious illness including but not limited to ongoing or active infection, symptomatic congestive heart failure, unstable angina pectoris, and/or cardiac arrhythmia.

3. Psychiatric illness/condition likely in the judgment of the Principal Investigator (PI) to limit compliance with clinical study requirements.

 |

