## 3.0 ENDPOINTS

### 3.1 Primary endpoint

Progression-free survival (PFS): Patients will be evaluated at least annually and at the discretion of the treating Investigator. PFS is defined as the time from 20030165 enrollment until documented disease progression or death (by any cause, in the absence of progression). In progression-free patients, PFS will be censored at the last evaluable tumor assessment (clinical, hematologic, and/or radiographic).

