### 3.2 Secondary endpoints

Progression-free survival (PFS): Patients will be evaluated at least annually and at the discretion of the treating Investigator. PFS is defined as the time from 20030165 enrollment until documented disease progression or death (by any cause, in the absence of progression). In progression-free patients, PFS will be censored at the last evaluable tumor assessment (clinical, hematologic, and radiographic).

Overall survival (OS): Patients will be evaluated at least annually. OS is defined as the elapsed time from 20030165 enrollment to death or date of censoring. Patients alive or lost to follow-up will be censored at the last date of contact (or last date known to be alive).

Response rate (RR): Patients will be evaluated at least annually or more frequently as clinically indicated and at the Investigator's discretion. Response rate is defined as the percentage of patients whose cancer shrinks or disappears after treatment.

Toxicity: Monitoring of AEs including serious adverse events (SAEs). AEs will be assessed in terms of nature, grade and attribution to treatment, using the National Cancer Institute Common Terminology Criteria for Adverse Events (NCI CTCAE), Version 3.0. Patients on maintenance thalidomide (THALOMID®) will be evaluated for adverse events (AEs) continually while on study.

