#### 12.4.1 Annually (every 12 months, ±30 days)

- Survival: contact by telephone or in-person visit; Methods used for attempted contact must also be documented properly.

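### The illness exclusion in Section 5.2.2 bars patients in every group from a study that is mostly survival follow-up; if any survivor is refused entry, long-term OS, and PFS in those still progression-free, could be distorted

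*Protocol*

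**What the plan says.** The primary objective (Section 2.1) is long-term follow-up of 20030165 patients, with or without continued thalidomide. The synopsis expects 2 patients in Group A (on thalidomide), 12 in Group B (complete response, no thalidomide) and 8 in Group C (died or progressed).

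The exclusions are not restricted to any group, and they appear in two forms:

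- **Synopsis:** "Uncontrolled, intercurrent serious illness including but not limited to ongoing or active infection, symptomatic congestive heart failure, unstable angina pectoris, and/or cardiac arrhythmia", with no further condition.
- **Section 5.2.2:** the same list, which opens "Uncontrolled, intercurrent serious illness including but not limited to ongoing or active infection, symptomatic congestive heart failure", followed at its end by "likely in the judgment of the PI to interfere with clinical study requirements". The grammar leaves open whether this governs the whole list or only arrhythmia.
- **Section 5.2.3:** "Psychiatric illness/condition likely in the judgment of the PI to limit compliance with clinical study requirements".

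Section 4.0 says: "Patients enrolled on the 20030165 clinical trial are eligible for this trial and will be offered enrollment to this study". Section 6.0 requires every eligibility requirement to be checked before entry.

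The follow-up burden off drug is light. Group B has a yearly physical examination and blood tests (Section 12.3.1). For Group C, Section 12.4.1 asks only for "Survival: contact by telephone or in-person visit".

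PFS and OS both run from 20030165 enrollment. Death without progression is a PFS event. PFS is censored at the last evaluable assessment, and OS at last contact or the last date known alive (Sections 3.1 and 3.2). The evaluable sets in 3.1.1 and 3.2.1 are eligible 20030165 subjects who received that trial's therapy. Group C, including those who died on 20030165, enters all analyses (synopsis and Section 7.0). Section 15.0 plans no formal analysis, but allows integration with the 20030165 analyses if the principal investigator thinks it necessary.

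**The concern.** An illness exclusion has an evident purpose where patients are about to receive a drug. It has little where the only study activity is a yearly visit or telephone call, which is the position of 20 of the 22 expected patients. Here it works against the stated objective, because a 20030165 survivor who fails 5.2.2 has no follow-up under this protocol.

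The statistical issue is which patients it removes. Uncontrolled serious illness plausibly raises the risk of death. Death is the OS event and, without progression, a PFS event. Censoring a patient near rollover because of such illness ties censoring to prognosis, while deaths that occurred earlier on 20030165 are all counted.

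The wording problem needs no assumption: the synopsis, Section 5.2.2 and Section 4.0 do not describe the same entry rule.

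Section 5.2.3 is a lesser matter. It turns on compliance, and nothing in the protocol links it to mortality. The point there is only that it needlessly removes patients from low-burden follow-up.

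**Working it through.** **Reproducing the plan's count.** Group A + Group B = 2 + 12 = 14, which matches the rollover figure in Section 7.0. With Group C, 14 + 8 = 22. Patients not on drug: 12 + 8 = 20.

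**Assumptions (not in the protocol).** All 14 Group A/B patients are event-free at rollover, and nobody was censored earlier. For PFS, all 8 Group C patients have had an event by the group's definition. For OS, taking all 8 as dead is an assumption. Let *k* of the 14 be refused entry, and let *s1* and *s2* be the 5-year event-free proportions after rollover for enrolled and refused patients.

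**Formulas.**

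- Everyone followed: [(14 − k)·s1 + k·s2] / 22
- Refused patients kept and censored at rollover: (14/22)·s1
- Refused patients dropped from the set: (14 − k)·s1 / (22 − k)

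The censoring bias is the second line minus the first: k·(s1 − s2)/22. It is positive whenever s2 < s1, zero when k = 0, and never more than k/22.

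**Ceiling for one or two patients** (every refused patient dies, every enrolled patient stays event-free). The estimate stays at 14/22 = 63.6%.

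- k = 1: true value 13/22 = 59.1%, bias +4.5 points
- k = 2: true value 12/22 = 54.5%, bias +9.1 points

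**A less extreme case** (assumed k = 2, s1 = 0.80, s2 = 0.40).

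- Everyone followed: (12 × 0.80 + 2 × 0.40)/22 = 10.4/22 = 47.3%
- Censored: 14 × 0.80/22 = 11.2/22 = 50.9%, bias +3.6 points
- Dropped: 12 × 0.80/20 = 9.6/20 = 48.0%, bias +0.7 points

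**Range over assumed values** (k = 1 to 4, s1 = 0.70 to 0.90, s2 = 0.20 to 0.60).

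| Handling of refused patients | Smallest | Largest |
|---|---|---|
| Censored | 1 × (0.70 − 0.60)/22 = +0.5 | 4 × (0.90 − 0.20)/22 = +12.7 |
| Dropped | −3.8 (k = 4, 0.70, 0.60) | +5.5 (k = 4, 0.90, 0.20) |

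The dropped extremes are 7.0/18 − 9.4/22 = 38.9% − 42.7% and 9.0/18 − 9.8/22 = 50.0% − 44.5%.

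Dropping also lowers the figure at rollover itself. With k = 2 it becomes 12/20 = 60.0% instead of 63.6%, because survivors leave the denominator and the dead stay.

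**Which endpoint is touched.** Only patients still progression-free can carry PFS bias. A living Group C patient has already had a PFS event, so refusing that patient affects OS only.

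**The case against.** A reader might infer that the exclusions do bias OS and PFS upward, by removing the patients closest to death. The documents do not support that much.

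- **No affected patient is shown.** Section 7.0 already describes the 14 rollover patients as eligible, and the expected counts set nobody aside. This stands: the effect is possible, not demonstrated.
- **The body wording may exclude hardly anyone.** If the investigator-judgment clause governs the whole list, interference with a yearly telephone call is hard to argue. This also stands, but it leaves the stricter synopsis version in place, and hence the need to reconcile the two.
- **The direction is not fixed.** Sections 3.1.1 and 3.2.1 do not say under which protocol a subject must be *eligible*. Eligibility for 20030165 is the more natural reading and leads to censoring. Eligibility for this study would lead to dropping, where either sign is possible.
- **Follow-up may continue elsewhere.** The 20030165 protocol is not at hand, and OS censoring accepts the last date known alive. A refused patient's status might still be learned, though nothing in this protocol arranges it.
- **The bar acts at entry only.** Illness arising later does not end follow-up under Section 8.6, and Section 11.0 lists later adverse events only for Group A. An infection may resolve, and nothing prevents later entry.
- **Section 4.0 may only name the recruitment pool,** with Section 6.0 supplying the eligibility check. That is fair; the sentence still reads as unconditional eligibility and should be aligned.
- **No formal analysis is planned.** Section 15.0 limits the consequence, but PFS and OS remain named endpoints and integration is left open.

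**Conclusion.** The point holds in a limited form. An illness exclusion suited to a treatment trial applies to all groups although 20 of 22 expected patients receive no drug. Its two versions can admit different patients, and the protocol makes no provision for following a survivor who fails it.

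The effect on estimates is conditional. If refused patients stay in the set and are censored near rollover, and their prognosis is worse, OS could be too high, as could PFS for those still progression-free. The ceiling is 4.5 points for one patient and 9.1 for two; smaller shifts are more plausible, such as 3.6 points in the assumed two-patient case. If they are dropped, the sign is open. If nobody is refused, there is no bias. The effect matters only if results are reported or integrated with 20030165.

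The survival and *k* values are assumptions. The mortality argument does not extend to Section 5.2.3.

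**What to change.** State in Section 5.2 and the synopsis that 5.2.2 and 5.2.3 do not bar enrollment for follow-up and survival contact. This should cover Groups B and C, and the follow-up of any Group A candidate. How the criteria bear on receiving thalidomide is a clinical matter for the sponsor to settle.

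Reconcile the synopsis and body wording of 5.2.2, make clear which conditions the investigator-judgment clause governs, and align Section 4.0 with the result.

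The cost is a wording amendment; no procedure is added beyond the yearly contact already planned. A small downside is that some patients may miss the yearly examination and contribute survival data only.

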## 6.0 Enrollment Procedures

To enter a patient, the Investigator or Study Team will contact the Clinical Research Services' (CRS) Representative. All eligibility requirements must be reviewed prior to the patient entering the study. The following information must be provided to the CRS Representative:

- 1) Completed and signed protocol-specific eligibility checklist;
- 2) All pages of the original signed informed consent form (ICF) including HIPAA Form B;
- 3) Relevant source documents *such as*: subject medical history and physical exam, admission or discharge notes, diagnostic reports, pathologic confirmation of diagnosis, and relevant subject-specific written communication.

